1.2 Rationale for study design, doses and control groups

This phase 3 study was intended to be included in applications for marketing authorization in the countries where the study is performed. ZS was approved in China for hyperkalemia based on overseas data at the end of 2019, now this is a post-approval commitment study for China.

A double-blind, placebo-controlled, randomized study represents the optimal design for obtaining unbiased estimates of treatment group differences for a new drug under development. Recognizing that all patients will receive active treatment during the open-label initial phase, combined with the fact that all patients will be monitored in the clinic for at least 4 hours after the initial dose of ZS, the level of hyperkalemia that could be included is not limited.

The randomized portion of the study (the 28-day randomized treatment study phase) is designed to assess whether extended administration of ZS maintains control of S-K values and to demonstrate that hyperkalemia recurs once ZS is withdrawn. Such design represents state-ofthe-art in demonstrating the need for ongoing longer-term treatment of a new drug under development. A 28-day randomized treatment study phase is selected as a compromise between ensuring a sufficiently long treatment period to demonstrate that ZS can maintain normokalemia over extended time, while not exposing patients with a potentially life-threatening condition to extended treatment with placebo. Eligibility for the open-label initial phase, eligibility for the 28-day randomized treatment study phase, and potassium-related stopping criteria are based on i-STAT measurements as these decisions need to be made in 'real-time' due to the risk of potentially life-threatening cardiac arrhythmias associated with severe hyperkalemia or hypokalemia. However, all endpoint analyses will be based on standardized S-K measurements analyzed at a central laboratory. For treatment decisions (i.e., S-K values on i-STAT < 3.5mmol/L), a second i-STAT sample will be taken 10 minutes after the initial abnormal sample to ensure that treatment is only changed once hypokalemia is confirmed. For a treatment decision to be made, both samples, taken 10 minutes apart, need to be below 3.5 mmol/L.

[figure not shown]

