3.9 Discontinuation of investigational product

Patients may be discontinued from investigational product (IP) in the following situations:

- Patient decision. The patient is at any time free to discontinue treatment, without prejudice to further treatment.
- Adverse Event

Clinical Study Protocol Drug Substance ZS Study Code **D9480C00001** Version **6.0** Date **19** August 2020

- Severe non-compliance with the study protocol
- Risk to patient as judged by investigator
- Pregnancy
- Require treatment with medications prohibited or contraindicated for use due to safety concerns with ZS
- Start dialysis while in the study
- Patient unblinded due to emergency
- Patients who change or switch RAAS inhibitor and/or diuretic dose during the study
- Patient develops severe hypokalemia (i-STAT potassium values <3.0 mmol/L) at any time during the study or has i-STAT level > 6.2 mmol/L during the 28-day randomized treatment study phase (confirmed by taking a second potassium measurement after a 10 ± 2-minute interval, and both i-STAT values meet the study drug discontinuation rule). Patients discontinuing due to this criterion must immediately receive appropriate medical treatment to manage their hypo- or hyperkalemia.
- Patient has a clinically significant cardiac arrhythmia (see below) at any time in the 28day randomized treatment study phase, the patient should immediately receive appropriate medical treatment and be discontinued from study drug. Any of the following cardiac events will result in immediate discontinuation from the study drug (independent of whether it is in the open-label initial phase or the 28-day randomized treatment study phase):
 - Serious cardiac arrhythmias (ventricular tachycardia or ventricular fibrillation, new atrial fibrillation or atrial flutter, new paroxysmal supraventricular tachycardia [other than sinus tachycardia], new 2nd or 3rd degree AV block or significant bradycardia [HR < 40 bpm])
 - Acute heart failure
 - Significant increase in PR interval (> 250 msec in the absence of pre-existing atrioventricular block), widening of the QRS complex (>140 msec in the absence of pre-existing bundle branch block) or new onset peaked T-wave

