- 18. The defined wider visit window can be applied, if patients are not able to strictly follow the pre-specified visit schedules, due to a prolonged public holiday.

Study Visit	Rand. Visit	Visit 6	Visit 7	Visit 8	Visit 9	Visit 10	Visit 11	Visit 12	Visit 13	Visit 14	EOS 9
28-day randomized treatment study phase Day ⁷	Day 1 ¹²	Day 2 ¹²	Day 5 ¹²	Day 8 ¹²	Day 12 ¹²	Day 15 ¹²	Day 19 ¹²	Day 22 ¹²	Day 26 ¹²	Day 29 ¹²	Day 35 ¹²
Accepted visit window during prolonged public holidays ⁸			Day 3-6	Day 7-9	Day 10-13	Day 14-17	Day 18-20	Day 21-24	Day 25-27	Day 28-31	Day 32-43
Eligibility criteria	Х										
Physical exam including weight ^{3, 13}	Х					Х				Х	Х
Access IVRS/IWRS ¹⁰	Х			Х		Х		Х			
Study drug (IP) dispensation ¹¹	Х			Х		Х		Х			
Study drug (IP) administration ⁴	Х	Х	Х	Х	Х	Х	Х	Х	Х		
ECG ³	Х			Х		Х		Х		Х	Х
Vital signs ³	Х					Х				Х	Х
Concomitant medications	Х	Х	Х	Х	Х	Х	Х	Х	Х	Х	Х
Adverse events (including SAEs)	Х	Х	Х	Х	Х	Х	Х	Х	Х	Х	Х
Potassium ⁶	X^2	Х	Х	Х	Х	X^2	Х	Х	Х	X^2	X^2
Clinical chemistry ^{1,3}	Х					Х				Х	Х
Hematology ^{1,3}	Х					Х				Х	Х
Urinalysis 1,3	Х					Х				Х	Х
Urine HCG											X^5
IP Reconciliation										Х	

Table 2Study Plan detailing the procedures: 28-day randomized treatment study phase

1. Parameters to be measured are detailed in Table 3.

2. Potassium will be measured fasting prior to the 1st daily dose as part of the clinical chemistry panel on Day 1, 15, 29, 35 in the 28-day randomized treatment study phase.

3. Physical Exam, ECG, Vital signs, weight, urinalysis, clinical chemistry including S-Aldo and P-Renin, and hematology parameters will be measured fasting (nothing by mouth except water for a minimum of 8 hours prior to potassium sample collection at the clinic); On the 28-day randomized treatment study phase Days 1,15, 29, and 35(EOS), blood sample which including S-Aldo and P-Renin test need to be collected prior to 10am after the patient has been upright for at least 2 hours and before the ECG.

4. Study drug will be administrated in the clinic on Day 1,2,5,8,12,15,19,22 and 26. If a patient develops i-STAT potassium values between 3.0 mmol/L and 3.4 mmol/L, inclusive (confirmed by taking a second potassium

measurement after a 10 ± 2 -minute interval, and both i-STAT values meet the study drug adjustment rule), dosing will be reduced from qd to every other day for the remainder of the study.

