If a patient develops i-STAT potassium values between 3.0 mmol/L and 3.4 mmol/L, inclusive (confirmed by taking a second potassium measurement after a 10 ± 2 minute interval), during the 28-day randomized treatment study phase, dosing will be reduced from qd to qod for the remainder of the study.

Patients with confirmed potassium <3.0 mmol/L in both study phases should discontinue from therapy as per Section 3.9.

Patients with confirmed i-STAT potassium >6.2 mmol/L during the 28-day randomized treatment study phase should discontinue from therapy as per Section 3.9.

For doses administered in the clinic during both study phases each dose will be individually dispensed by designated, trained site staff.

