5.3	Incorrect Dose Adjustment during Open Label Phase: If a patient develops confirmed i-STAT potassium values between 3.0 mmol/L and 3.4 mmol/L, inclusive, during the open-label initial phase, but patient takes more ZS during the rest of that day. (refer to CSP sec. 7.2)	CSP v6.0 (19-Aug-2020)	- B&I Programming - Source Data review	LB: LB1: EX
5.4	Incorrect dose adjustment during 28-Day Randomized Treatment Phase: If a patient develops i-STAT potassium values between 3.0 mmol/L and 3.4 mmol/L, inclusive (confirmed by taking a second potassium measurement after a 10 ± 2 minute interval), during the 28 -day randomized treatment study phase, dosing is not reduced from qd to qod for the remainder of the study.	CSP v6.0 (19-Aug-2020)	- Source Data review	-
5.5	Incorrect dose adjustment during 28-Day Randomized Treatment Phase: After dosing reduced from qd to qod, if a patient i-STAT potassium value is back to normal (3.5 – 6.2 mmol/L inclusive), during the 28-day randomized treatment study phase, dosing is increased back from qod to qd for the remainder of the study.	CSP v6.0 (19-Aug-2020)	- Source Data review	
5.6	Use of expired IP	CSP v6.0 (19-Aug-2020)	- Source Data review	
6	Excluded Medications taken			

STATISTICAL ANALYSIS PLAN

6.1	Subject received concomitant medication defined as	CSP v6.0	- Manual Physician Review	СМ
	prohibited in the CSP (corporate IPD).	(19-Aug-2020)	based on CMR/GPR reports	
	Administration of prohibited concomitant medication or non-		- B&I Programming	
	drug therapy as outlined in CSP sec 7.7)		- Source Data Review	
7.	Deviations to study procedure			
7.1	Two or more successive visits missed or not performed	CSP v6.0	- B&I Programming	VISIT, VISIT1
	according to the protocol	(19-Aug-2020)	- Source Data Review	
7.2	Any of the following visits missed:	CSP v6.0	- B&I Programming	VISIT, VISIT1
	For those patients randomized (with patient randomization	(19-Aug-2020)	- Source Data Review	
	number) on Day 2 and get randomized same day, they should			
	complete:			
	- Enrolment/screening visit			
	- Open label initial phase Day 1			
	- Randomization visit			
	For those patients randomized (with patient randomization			
	number) on Day 3 they should complete.			
	- Enrolment/screening visit			
	- Open label initial phase Day 1			
	- Open label initial phase Day 2			
	- Randomization visit			
	For those patients who failed OLP, they should complete:			
	- Enforment/screening visit			

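### In the randomised phase the protocol's passages disagree on what the second i-STAT reading must show, and 2.9 then 3.1 mmol/L triggers neither the stop nor the dose reduction

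*Protocol*

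**What the plan says.** Dosing decisions on potassium use i-STAT, with a confirming reading 10 ± 2 minutes after the first.

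- **Stop.** CSP 3.9 lists "Patient develops severe hypokalemia (i-STAT potassium values <3.0 mmol/L) at any time during the study" as a ground for discontinuing drug, on condition that "both i-STAT values meet the study drug discontinuation rule". Figure 4 note 2 repeats the condition.
- **Reduction, strict wording.** Table 2 note 4 opens "If a patient develops i-STAT potassium values between 3.0 mmol/L and 3.4 mmol/L, inclusive" and adds that "both i-STAT values meet the study drug adjustment rule".
- **Reduction, looser wording.** The synopsis, CSP 7.2 and Figure 4 note 4 use the same band and ask for a second measurement as confirmation, after which "dosing will be reduced from qd to qod for the remainder of the study". They do not say what the second value must be.
- **General test.** CSP 1.2: "For a treatment decision to be made, both samples, taken 10 minutes apart, need to be below 3.5 mmol/L". It does not say which decision follows.
- **Other provisions.** CSP 3.9 also allows discontinuation for "Risk to patient as judged by investigator". CSP 5.2.3 calls for an additional ECG when i-STAT potassium is below 3.0 and states no confirmation condition.
- **SAP.** In Appendix A, deviation code 3.10 copies the CSP 3.9 rule. Code 5.4 covers a 3.0 to 3.4 patient for whom "dosing is not reduced from qd to qod for the remainder of the study". Code 5.3 is the open-label counterpart.

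**The concern.** The stop and the reduction are meant to be adjacent bands that meet at 3.0 mmol/L. Because each band also requires both readings to fall inside it, a pair with one reading on each side of 3.0 belongs to neither. CSP 1.2 nevertheless counts such a pair as sufficient for a treatment decision.

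Hypokalaemia is one of the two risks identified for the drug, and CSP 1.3.3 relies on potassium monitoring and dose adjustment to mitigate it. The unassigned pairs lie at the boundary of what the protocol calls severe. Sites using different passages could act differently on the same readings. SAP codes 3.10 and 5.4 inherit the same bands, so neither clearly says what counts as a deviation for these patients.

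**Working it through.** There is no planned figure to reproduce; this is a check of rule logic. Readings are taken to 0.1 mmol/L, which is an assumption consistent with the adjacent cut-offs of 3.4 and 3.5.

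For a first reading a and a second reading b:

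- Confirmed (CSP 1.2): a < 3.5 and b < 3.5
- Stop (CSP 3.9, Figure 4 note 2): a < 3.0 and b < 3.0
- Reduce, strict (Table 2 note 4): a and b both within 3.0 to 3.4
- Reduce, looser (synopsis, CSP 7.2, Figure 4 note 4): a within 3.0 to 3.4, with b confirming in a sense not stated

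| First, second | Confirmed | Stop | Reduce, strict | Reduce, looser |
|---|---|---|---|---|
| 3.4, 3.4 | yes | no | yes | yes |
| 2.9, 2.9 | yes | yes | no | no |
| 2.9, 3.1 | yes | no | no | no, read literally |
| 3.1, 2.9 | yes | no | no | arguable |

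The last cell is arguable because confirmation could mean a second value in the band (not met) or, borrowing from CSP 1.2, a second value below 3.5 (met).

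**Is this the only gap?** From 2.5 to 3.4 there are 10 possible readings, so 10 × 10 = 100 ordered pairs, all confirmed under CSP 1.2. Five readings are below 3.0 and five are within 3.0 to 3.4. Stop takes 5 × 5 = 25 pairs, strict reduction takes 5 × 5 = 25, and 100 − 25 − 25 = 50 get neither. All 50 have one reading on each side of 3.0, so there is no other gap. These are grid cells, not probabilities.

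**Time to the next check.** From Day 2 the scheduled potassium visits are Days 2, 5, 8, 12, 15, 19, 22, 26 and 29, which are 3 or 4 days apart. On the nominal schedule, a patient left on the default would next be measured after that interval.

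**Open-label phase.** On Day 2, CSP 4.3.2 gives further drug only at 5.1 or above, randomises only at 3.5 to 5.0, and refers lower values to CSP 7.2. On Day 3, CSP 4.3.3 discontinues study medication below 3.5. That leaves essentially Day 1 after dosing, where CSP 4.3.1 refers values below 3.5 to CSP 7.2, and CSP 7.2 holds that day's remaining doses only for confirmed 3.0 to 3.4. Entry needs two readings of at least 5.1, so a Day 1 reading below 3.0 means a fall of more than 5.1 − 3.0 = 2.1 mmol/L. CSP 1.3.1 reports falls at 48 hours of 0.8, 1.2 and 1.5 mmol/L by baseline group.

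**Frequency.** CSP 1.3.2 reports potassium below 3.5 in 4.1% of treated patients. Applied to the 200 planned for active drug, 0.041 × 200 = 8.2. Figure 2 shows an excess of 9.8 (1.6, 18) at 10 g; if that is in percentage points, it is about 10 of 100 patients (roughly 2 to 18). Only patients near 3.0 can produce a mixed pair.

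The chance that a pair is mixed depends on repeat error, which the documents do not give. As an illustration only, assume independent normal error with SD 0.05 to 0.15 mmol/L:

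P(mixed) = 2 × P(reading ≤ 2.9) × P(reading 3.0 to 3.4)

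| True potassium | SD 0.05 | SD 0.10 | SD 0.15 |
|---|---|---|---|
| 2.95 | 0.50 | 0.50 | 0.50 |
| 3.0 | 0.267 | 0.427 | 0.465 |
| 3.1 | 0.003 | 0.125 | 0.264 |

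**The case against.** The strongest reply is that no patient is abandoned. A single reading of 2.9 calls for the ECG in CSP 5.2.3, which feeds the cardiac stopping criteria in CSP 3.9. The investigator may stop drug for judged risk or an adverse event. The strict condition for reduction appears in one table footnote, and the looser passages, read with CSP 1.2, arguably cover 3.1 then 2.9. The Figure 4 flow chart itself was not available for this check, only its notes, so a box in the chart might assign mixed pairs. The primary estimand uses a treatment policy strategy, and hypokalaemia is tabulated from laboratory values.

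Much of this stands, and it rules out several stronger readings:

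- A reader might infer that the protocol requires full once-daily dosing to continue, or that nothing at all happens. It does neither: continuation is a default, and the ECG and discretionary stop remain.
- A reader might infer that the open-label phase is equally exposed. CSP 4.3.2 and 4.3.3 largely close the gap on Days 2 and 3.
- A reader might infer that a quarter to a half of confirmations near 3.0 would be mixed. That rests on an assumed error and does not hold at 3.1, where the illustration gives 0.3% to 26%.
- A reader might infer that the deviation codes are unusable. Codes 3.4 (risk judged but drug not stopped) and 8.1 (unforeseen important deviations) remain.

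What the reply does not remove is the conflict in the text. Investigator discretion is a backstop. It does not supply the pre-specified action that two adjacent bands are meant to give, and the looser wording does not clearly cover 2.9 then 3.1.

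**Conclusion.** The point holds for the 28-day randomised phase. Four descriptions of what the second reading must show do not agree. Read literally, 2.9 then 3.1 passes the CSP 1.2 test and triggers neither dosing rule, while the milder pair 3.4 and 3.4 triggers a reduction. The result for 3.1 then 2.9 turns on which passage a site follows. In the open-label phase the same gap is essentially limited to Day 1 post-dose readings.

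Few patients are likely to be affected, possibly none, and the documents do not allow a trial-level frequency. The planned primary analysis is not altered. This is a matter of consistent safety conduct and deviation coding, worth correcting because the passages contradict one another on a stated safety rule. The conclusion assumes readings to 0.1 mmol/L and that the Figure 4 chart adds no rule beyond its notes.

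**What to change.** Reconcile the synopsis, CSP 1.2, 3.9 and 7.2, Table 2 note 4, Figure 4 (chart and notes 2 and 4), and SAP deviation codes 3.10, 5.3 and 5.4, so that every pair with both readings below 3.5 mmol/L maps to exactly one stated action in each phase. One way is to state which reading of the pair decides the band once both are below 3.5. Which reading governs, and what the action is, are for the sponsor's clinical team.

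The cost is one sentence repeated in the listed places, by amendment or site memo. No extra samples are needed, because the second reading is already taken. If dosing has finished, the deviation coding can still be clarified in the review that SAP 3.3.8 places before database lock.

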4.2 Enrolment/screening period (Visit 2)

Study procedures will be performed according to the Study Plan in Table 1.

At screening, consenting patients are assessed to ensure that they meet eligibility criteria. Patients who do not meet these criteria must not be entered in the study.

Patients can be re-screened once during the clinical trial period. A new ICF does not need to be signed before re-screening if the original ICF was signed within 30 days and has not been revised.

After a patient has signed the ICF for the screening part of the study at Visit 2 the site investigator will use the IVRS/IWRS to obtain a unique patient enrolment number after collecting the demographic parameters from the patient (including sex, date of birth, race, ethnic group).

4.3 Treatment Period

Table 1 and Table 2 provide an overview of the procedures performed at each visit during the treatment period, and further details are provided below. Changing the order of the procedures at a visit, e.g., for logistical reasons, would not constitute a protocol violation if agreed in advance and in writing between the site and the sponsor study physician.

4.3.1 Open-label initial phase Day 1 (Visit 3)

Patients will arrive in the morning, fasting (nothing by mouth except water for a minimum of 8 hours prior to potassium sample collection at the clinic).

The following assessment will be performed:

- Review and confirm the patient's eligibility for the study by assessing inclusion and exclusion criteria listed in Sections 3.1 and 3.2.
- Two potassium samples for assessment, using both i-STAT and the Central Laboratory, will be collected 60 minutes (± 10 min) apart.
- If either i-STAT potassium value is <5.1 mmol/L the patient will be declared a screen failure and withdrawn from the study.
- If both i-STAT values are ≥ 5.1 mmol/L the following samples will be collected:
 - A blood sample for standard assessment of hematology and clinical chemistry
 - Urine for standard assessment of urinalysis parameters including a pregnancy test if the patient is a woman of childbearing potential
- Obtain vital signs (pulse rate and blood pressure)
- Patient medical and surgical history including co-morbidities (over previous 6 months) will be obtained with the review of selection criteria
- Perform 12-lead Electrocardiogram (ECG)
- Perform a complete physical examination including weight, see Section 5.2.2;
- Review and record the concomitant medications and AEs/SAEs

Note: The above procedures should be performed within 1 day of the first administration of study drug and before any IP administration.

Patients who meet all inclusion/exclusion criteria will be entered into the trial and the following procedures will take place:

- The site will access the IVRS/IWRS and the system will assign the patient an openlabel initial phase IP kit
- The first doses of study IP will be administered as a slurry/suspension in water. The patient will be shown/instructed on how to mix and administer the IP
- 1 hour (± 15 min) after dose administration a blood potassium sample (i-STAT and Central Laboratory) will be collected, following which the patient is allowed to break the fast
- Two additional blood potassium samples (i-STAT and Central Laboratory) will then be taken at 2 and 4 hours (±15 min) after dose administration.

- Patients with i-STAT potassium levels < 6.1 and ≥ 4.0mmol/L at the 4 hour (± 15 minutes) post Dose 1 blood draw will be sent home with instructions on how to take the IP. They will be requested to fill out a dosing schedule card indicating when they took the IP. The patient will return to the clinic the following morning for the open-label initial Phase Day 2 (Visit 4)
- Patients with i-STAT potassium ≥ 6.1 or < 4.0 mmol/L at the 4 hour post Dose 1 blood draw will stay in the clinic and take the second dose of study drug approximately 4-hours after the first dose. They will then remain in the clinic an extra 90 minutes (± 15 minutes) after taking the second dose when another blood sample for potassium determination (i-STAT and Central Laboratory will be collected and an ECG will be recorded).
- If i-STAT potassium levels are > 6.2 mmol/L as determined by the i-STAT at the 90minute post Dose 2 blood draw, the patient will be discontinued from the study. Patients will return to the clinic 7 (±1) days later for an EOS visit.
- If i-STAT potassium levels are ≤6.2 mmol/L and the ECG does not show any of the ECG withdrawal criteria, the patient will be sent home with the third dose of study drug and the dosing card and return to the clinic in the morning of the open-label initial phase Day 2 (Visit 4).
- See Section 7.2 regarding how to handle patients with potassium < 3.5mmol/L.

4.3.2 Open-label initial phase Day 2 (Visit 4)

Patients will arrive fasting at the clinic in the morning (nothing by mouth except water for a minimum of 8 hours prior to potassium sample collection at the clinic). They will bring the used and/or unused IP and completed dosing schedule card with them.

- The clinic staff will solicit any AEs, note any changes in concomitant medications, examine the IP and make note of the time the doses were taken and any unused IP on the eCRF and source documents.
- Potassium levels will be evaluated by i-STAT and the Central Laboratory. i-STAT potassium measurement will be done during the visit to determine the next steps of procedures.
 - If the i-STAT potassium value is < 3.5mmol/L, see Section 7.2 regarding how to handle patients.
 - If the i-STAT potassium value is between 3.5 and 5.0 mmol/L inclusive the patient will skip the remaining procedures for initial phase Day 2 and will be randomized (on the same day) into the 28-day randomized treatment study phase, and complete the remaining procedures detailed in Section 4.3.4. In this case Visit 4 will be skipped completely and the patient will conduct the Randomization visit instead. No data entry is done in the Visit 4 eCRF.

- If the i-STAT potassium value is \geq 5.1 mmol/L, the patient will receive an additional 24 hours of ZS 10g TID and the following procedures will be performed.
- An ECG will be performed (Section 5.2.3)
- Following completion of the above procedures, the first daily dose of IP will be administered in the clinic as a slurry/suspension in water, followed by the 1 hour post Dose 1 blood draw (see Figure 4 for the flow chart based on the potassium value), after which the patient is allowed to break the fast.
- Patients will then be sent home with study drug and instructions on how to take the IP. They will be requested to fill out a dosing schedule card indicating when they took the IP.
- Patients will return to the clinic the following morning and bring the used and/or unused IP and completed dosing schedule card with them.

4.3.3 Randomization Visit - For patients not entering the 28-day randomized treatment study phase

On Day 3 of the Open-Label initial phase, patients will arrive at the clinic in the morning, fasting (nothing by mouth except water for a minimum of 8 hours prior to potassium sample collection at the clinic). They will bring the used and/or unused IP and completed dosing schedule card with them.

- The clinic staff will solicit any AEs, note any changes in concomitant medications, examine the IP and make note of the time the doses were taken and any unused IP on the eCRF and source documents.
- Vital signs (pulse rate and blood pressure) will be obtained.
- Potassium levels will be evaluated by i-STAT and the Central Laboratory.
 - If the i-STAT potassium value is within the normal range (3.5 to 5.0 mmol/L, inclusive) the patient will be randomized into the 28-day randomized treatment study phase and complete the procedures detailed in (Section 4.3.4).
 - However if the i-STAT potassium value is > 5.0 mmol/L or < 3.5 mmol/L the below assessments will be performed:
 - Samples will be collected: Blood samples for the standard assessment of clinical chemistry; blood sample for standard assessment of hematology; Urine for standard assessment of urinalysis parameters
 - An ECG will be performed (Section 5.2.3)
 - Perform physical examination including weight (Section 5.2.2)

- Withdraw the patient from the open-label initial phase and access IVRS/IWRS to register subject as not randomized.
- Patients will then DISCONTINUE from the study medication, and receive standard of care at the discretion and the direction of his/her own physician. However, the patient will need to return to the clinic 7 (\pm 1) days later for an EOS visit in the morning, fasting, nothing by mouth except water (Section 4.4).

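### The stop for potassium above 6.2 mmol/L is stated inconsistently for the open-label phase, and the SAP ties a randomized-phase event to an open-label blood draw

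*Protocol*

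**What the plan says.** **Open-label Day 1 (Protocol 4.3.1).** Patients whose i-STAT potassium is 6.1 or more, or below 4.0, four hours after the first dose "will stay in the clinic and take the second dose of study drug approximately 4-hours after the first dose". They have a further draw 90 minutes later. If that value is above 6.2, "as determined by the i-STAT at the 90minute post Dose 2 blood draw, the patient will be discontinued from the study". No repeat reading is mentioned.

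**Discontinuation section (Protocol 3.9).** The criterion is that the patient "has i-STAT level > 6.2 mmol/L during the 28-day randomized treatment study phase". It needs a second reading after 10 ± 2 minutes, with both readings meeting the rule. The consequence is discontinuation of investigational product.

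**Dosing section (Protocol 7.2).** "Patients with confirmed i-STAT potassium >6.2 mmol/L during the 28-day randomized treatment study phase should discontinue from therapy as per Section 3.9". The synopsis, Figure 4 note 3 and SAP Appendix A, IPD 3.10, carry the same phase limit and the same need for confirmation.

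**Open-label Day 2 (Protocol 4.3.2).** At an i-STAT value of 5.1 or more, "the patient will receive an additional 24 hours of ZS 10g TID and the following procedures will be performed". Table 1 note 8 (above 5.0), and Section 7.2 for patients retested after a low Day 1 value (5.1 or more), also continue without an upper value. For the draw one hour after the Day 2 dose, the text points to Figure 4.

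**SAP 4.2.3.2.** For time to hyperkalemia, subjects who stop treatment in the randomized treatment phase (RTP) because of high potassium count as events. The SAP describes that potassium criterion as an i-STAT value above 6.2 at the 90-minute draw after dose 2.

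**The concern.** A numeric stopping threshold should read the same wherever it appears, or the plan should say why it differs by phase. Here the open-label stop appears only in a visit description. The section that lists the reasons for stopping the drug restricts the same threshold to the other phase and adds a confirmation step.

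Protocol Section 1.2 places no limit on entry potassium, so values above 6.2 can occur in the open-label phase. Sites need to know at which open-label draws the threshold applies and whether to repeat the sample.

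The uncertainty has already reached the analysis plan. The SAP clause sits in the event definition for time to hyperkalemia, which supplies tests 8 and 9 of the confirmatory sequence (SAP Table 3). As written, its condition cannot occur in the phase that it describes.

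**Working it through.** The plan states no figure on this point to reproduce. The check sets the passages side by side for one value, 6.4 mmol/L on i-STAT.

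| Time point | What the text says at 6.4 | Confirmation | Consequence | Source |
|---|---|---|---|---|
| Day 1, 4 h after dose 1 | 6.1 or more: stay in clinic, take dose 2 | none stated | continue | 4.3.1 |
| Day 1, 90 min after dose 2 | above 6.2: stop | none stated | off the study, EOS visit 7 ± 1 days later | 4.3.1 |
| Day 2, pre-dose | 5.1 or more: another 24 h | none stated | continue, subject to the other stops in 3.9 | 4.3.2; Table 1 note 8 |
| Day 2, 1 h after dose | pointer to Figure 4 | not visible | not visible | 4.3.2 |
| Day 3 | above 5.0: not randomized | none stated | off the drug, EOS visit | 4.3.3 |
| Randomized phase | above 6.2: stop | second reading after 10 ± 2 min | off the drug; assessments continue if the patient agrees | 3.9; 7.2; synopsis; Figure 4 note 3 |

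**Is the phase limit in 3.9 accidental?** Probably not. The same bullet applies the low threshold (below 3.0) at any time in the study, and the cardiac bullet names both phases. Section 3.9 includes the open-label phase explicitly when it means to. The Day 1 stop in 4.3.1 therefore has no counterpart there.

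**Who reaches the Day 1 check?** Only patients at 6.1 or more, or below 4.0, at four hours. The others go home until Day 2.

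**What does the SAP clause capture?**
1. The 90-minute draw after dose 2 exists only on open-label Day 1 (Protocol Table 1 note 4; Section 4.3.1). Randomized dosing is once daily, and the randomized-phase schedule in Table 2 has no such draw.
2. A patient above 6.2 at that draw is discontinued from the study under 4.3.1, so is not randomized and is not in FAS-RTP.
3. Read literally, the clause therefore captures nobody. Its apparent intent, discontinuation for confirmed i-STAT above 6.2 in the randomized phase, is not what it says.

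**Would this move tests 8 and 9?** The event is serum potassium of 5.1 or more. A patient stopped for i-STAT above 6.2 would lack an event only if the paired central-laboratory value were below 5.1, a gap between methods of more than 6.2 − 5.1 = 1.1 mmol/L, or if no usable serum value existed. On that reasoning the effect is probably small, but the documents give no count of such cases.

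**The case against.** The strongest reply is that most of this is silence, not conflict. Section 3.9 lists situations in which patients may be discontinued. It does not tell a site to keep dosing an open-label patient above 6.2. Section 4.3.1 is the only text on that particular draw, so a site can obey both sections, and the Day 1 and Day 2 instructions can be followed in sequence. A difference by phase may also be intended: Section 1.2 explains that everyone receives active drug in the open-label phase and is monitored for at least four hours, whereas the randomized phase includes placebo. All of this stands, so a reader who infers that the sections cannot both be obeyed goes too far.

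Three other strong inferences also fail:

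- **Day 2 dosing continues whatever the patient's state.** An ECG comes before the Day 2 dose, the cardiac and ECG stops in 3.9 apply in both phases, and so does investigator-judged risk. The Figure 4 drawing may also hold a Day 2 action. What can be said is that the readable Day 2 text states no potassium ceiling.
- **A missed Day 1 stop could not be flagged.** IPD 8.1 can take any important deviation that was not prespecified, and IPD 3.4 covers failure to stop despite investigator-judged risk. No dedicated IPD line names the Day 1 stop, and that is all.
- **The affected group is everyone not normokalemic at 24 hours** (Section 1.3.1 reports 77% normokalemic by then in ZS-004). That group includes every value outside the normal range. It is not the number above 6.2.

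The difference between leaving the drug and leaving the study is also narrower than it looks in this phase, because 3.9 too sends open-label discontinuations to an EOS visit 7 ± 1 days after the last dose.

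The reply does not explain why the open-label stop is absent from the section that lists the stops, or why confirmation is required in one place and not mentioned in the other. Nor does it touch the SAP clause.

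**Conclusion.** The point holds as an inconsistency in a stopping threshold, not as a set of orders that cannot all be obeyed. Three things differ between passages: the phase and time points at which above 6.2 stops a patient, whether a second reading is needed, and whether the patient leaves the drug or the study. In addition, SAP 4.2.3.2 describes a randomized-phase event by a draw that belongs to open-label Day 1. That is an error on the face of the text.

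The size cannot be given, because the documents do not report how many patients would exceed 6.2 at any open-label time point. A reader might infer bias in the open-label efficacy test. A patient stopped on Day 1 would have no end-of-OLP value under SAP Table 2 note 4, so uneven use of the rule could alter who contributes. Nothing in the documents shows that this would change a conclusion, and FAS-OLP keeps everyone who was dosed.

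The verdict assumes that the Figure 4 drawing does not settle the matter. If it shows an open-label action above 6.2, the Day 2 gap narrows, but 3.9, 4.3.2 and 7.2 still do not state it and the SAP clause is unaffected. This should be corrected. No view is taken on which clinical rule is right.

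**What to change.** Reconcile Protocol 3.9, 4.3.1, 4.3.2, 7.2, the synopsis and Figure 4, together with SAP IPD 3.10, so that they agree on:

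1. the time points at which a rule for values above 6.2 applies, stated for Day 1 after dose 2, Day 2 pre-dose, Day 2 one hour after the dose, and the randomized phase;
2. whether a confirmatory reading is needed at each;
3. whether the patient leaves treatment or the study.

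If the rules are meant to differ by phase, one sentence saying so, with a cross-reference from 3.9 to 4.3.1, would be enough. The content of the rule is for the sponsor and investigators to decide.

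In SAP 4.2.3.2, replace the reference to the 90-minute draw with the randomized-phase discontinuation criterion as finally worded, and state how such a patient is dated and counted when no serum value is available. Settle this before unblinding. If that point has passed, report how these cases were counted.

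The cost is clarification wording in the protocol, one IPD line and one SAP sentence. No visits, samples or staff are added.
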